1.2 Study Aims/Objectives

Primary Objective:

1. To assess the effects of 12 weeks of Entresto on the functional clinical parameters maximal walking duration, pain free walking duration and 6 minute walk test of patients with PAD.

Secondary Objective:

1. To assess if changes in functional clinical parameters are related to improvements in microvascular and mitochondrial function and to assess the effects of increasing NP activity on arterial elasticity.
2. To assess the time required for functional improvements (6 minute walk test) to return to baseline

values following 12 weeks of Entresto.

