3.6 Mitochondrial functional testing with magnetic resonance spectroscopy (MRS)

The bioenergetics of the medial gastrocnemius (MG) and soleus (Sol) muscle (Figure 2) will be assessed using MRS before, during and following a 24 seconds isometric maximal voluntary contraction (MVC). MRS will be performed in a 7 Tesla/90 cm whole-body actively shielded human scanner (Siemens AG, Erlangen, Germany). Optimal positioning of the muscle volume in the isocenter of the magnet will be determined using scout image scans with three orthogonal slices and multislice gradient echo images (matrix size = 108×128 , 14 slices, 7 mm slice thickness, field of view = $13 \times 16 \times 20$ cm, echo time (TE) = 5 ms, TR = 0.4 s)³⁷.

These scans will be used to identify the MG

and the Sol muscle (Figure 2) and positioned near the center of the ^{31}P coil for acquisitions of a time-resolved ^{31}P MR spectra. Acquisition of MRS will be performed using a pulse-acquire ^{31}P MRS sequence with a small ^{31}P surface coil (6 cm diameter) tuned to the resonance frequency of phosphorus at 7T (120.7 MHz). A nominal 90° square excitation pulse (pulse width of 300 ms) with TR of 1 s, an acquisition bandwidth of 5000 Hz and 2,048 data points will be used to acquire phosphorus data^{42,43}. MRS data will be quantified with jMRUI using the AMARES time domain fit routine⁴⁴. The following parameters will be acquired by MRS: PCr content and pH at rest and at the end of a 16 s isometric contraction, the rate constant of PCr recovery (KPCr) and maximal rate of oxidative phosphorylation (V_{max}).

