3.6.1 Advantage of high field MRS

Figure 3 shows the ^{31}P spectra acquired using the 7T at the Center for Magnetic Resonance Research of the University of Minnesota by [name] and his collaborators⁴⁵. Collecting ^{31}P -MRS data at 7T offers more than twice as much signal to noise ratio (SNR) per unit time thus reducing measurement time compared to 3T magnet⁴⁶. In addition, the increase in SNR allows the measurement of MRS parameters in muscles of interest and with high temporal resolution (1 s). This is important because the Sol, as a postural muscle, is predominantly a slow twitch muscle (slow fatigue, primary source of ATP is oxidative phosphorylation) and the gastrocnemius muscles, are more active during locomotion, is a 50% fast twitch muscle (fast fatigue and primary source of ATP is anaerobic glycolysis). The effects of PAD on each muscle may be different and the benefits from treatment will depend on the metabolic characteristics of each muscle. Therefore, measuring oxidative phosphorylation in each muscle separately will provide us with a more accurate assessment of the effects of Entresto on the bioenergetics of skeletal muscles in patients with PAD.

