3.8.1 Functional MRI data analysis

Images will be analyzed using custom-written Matlab version 7.0.1 (The Mathworks, Natick, MA) routines. The functional images will be co-registered to the anatomical image using a rigid registration procedure⁵⁷. Then the anatomical image will be used to identify the MG and Sol muscles and regions of interest (ROIs) will be specified separately around those two muscles. Resolved connective tissues and blood vessels will be excluded from the ROIs. The mean functional image SI for the ROI will be

calculated as a function of time and divided by the corresponding mean pre contraction SI value. An average SI time course will be obtained by averaging the SI time course from two trials, as previously described⁵⁶.

The averaged SI time course will be fitted to a polynomial function, and inflections in the derivative of this polynomial will be used to identify the minimum and maximum post contraction SI values. Figure 4 shows post contraction signal intensity indicating change in oxygenation plotted as a function of time. Data obtained at University of Minnesota CMRR 7T, unpublished observation. The change in SI ($\Delta SI = b - a$) will be determined for the Sol and MG muscle reflecting the average post contraction changes in oxygenation at the muscles microvascular bed.

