9.1 Statistical Methods

General baseline characteristics will be described using mean and proportions. Smirnov-Kolmogorov tests will be used to test normality of distribution of variables. For variables that do not follow the normal distribution, log transformation will be performed. Linear simple and multiple regressions will be performed to assess

association between the effects of Entresto on metabolic and physiological changes with clinical functional variables. Differences between the placebo and the

Entresto group will be assessed using independent sample t-test and Chi-square for quantitative and categorical variables, respectively. Change following the 12 week clinical trial in metabolic and physiological parameters will be assessed using paired sample t-test. Repeated measures analysis of covariance will also be used to evaluate differences between groups as a function of time. A p value < 0.05 will be used to determine statistical significance. Effect size (EF) calculated as $EF = (\text{mean Entresto group} - \text{mean placebo}$

group)/SD (control group) will be used to assess the clinical significance of the effects of Entresto⁶³. The PI will be in charge of performing all statistical calculations using SAS v 9.3 by SAS Institute Inc., Cary, NC. [name] Jr. Professor at the School of Public Health a statistician with more the 800 publications will be a consultant in statistical analysis of the data.

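### Section 9.1 tests the mechanistic objective with an undefined set of regressions, roughly 15 to 51 possible pairings, each at unadjusted p < 0.05 and none named as the main test

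*Combined protocol and SAP*

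**What the plan says.** Section 1.2 lists three walking measures under the primary objective: "functional clinical parameters maximal walking duration, pain free walking duration and 6 minute walk test of patients with PAD". Its first secondary objective is "To assess if changes in functional clinical parameters are related to improvements in microvascular and mitochondrial function", together with the drug's effect on arterial elasticity.

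For the link between the two, section 9.1 states: "Linear simple and multiple regressions will be performed to assess" the "association between the effects of Entresto on metabolic and physiological changes with clinical functional variables". The only decision rule is "A p value < 0.05 will be used to determine statistical significance". The section gives no number of regressions, model, covariates, lead marker, lead walking outcome or multiplicity adjustment.

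The candidate markers are spread over section 3:

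- **MRS (section 3.6):** "PCr content and pH at rest and at the end of a 16 s isometric contraction, the rate constant of PCr recovery (KPCr"), plus Vmax. That is six parameters.
- **Muscles for MRS:** section 3.6.1 argues for "measuring oxidative phosphorylation in each muscle separately". Section 3.8 instead describes a global MRS signal tuned mainly to the medial gastrocnemius.
- **fMRI (section 3.8.1):** the signal change "will be determined for the Sol and MG muscle reflecting the average post contraction changes in oxygenation". Section 3.8 runs the procedure with a gradient echo (GRE) and again with a spin echo (SE) sequence, and section 3.8.2 gives the two sequences different meanings.
- **Arterial elasticity:** radial tonometry, described in section 6.1.

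**The concern.** The objective is one question, but the plan allows it to be answered by any of many pairings, each carrying its own 5% error. If nothing defines which pairing decides, one significant result among dozens can be reported as the answer.

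The protocol gives this answer some weight. Section 1.1.4 says the study is to supply the supporting evidence on whether muscle function improves and goes with exercise tolerance. Section 1.1.5 says such measurements would give the biological grounds for recommending the drug in PAD. A chance association could therefore be presented as the mechanism behind a treatment effect.

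**Working it through.** **Figures in the plan.** The documents state no number of regressions and no family-wise error rate, so there is no figure to reproduce on this point. The sample size in section 9.2 does reproduce: taking 278 m as the difference and 240 m as the SD, two-sided 0.05, the noncentral t gives power 0.839 at 14 per group and 0.865 at 15. That calculation concerns pain free walking distance only.

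**Step 1: count the pairings.** Pairings m = markers × 3 walking outcomes (section 1.2). Expected false positives are 0.05m. If all tests are independent, the chance of at least one is 1 − 0.95^m.

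| Reading | Markers | m | 0.05m | 1 − 0.95^m |
|---|---|---|---|---|
| 6 MRS × 2 muscles + fMRI 2 muscles × 2 sequences + 1 elasticity | 12 + 4 + 1 = 17 | 51 | 2.55 | 92.7% |
| Same, without elasticity | 16 | 48 | 2.40 | 91.5% |
| MRS in one muscle, with elasticity | 6 + 4 + 1 = 11 | 33 | 1.65 | 81.6% |
| MRS in one muscle, without elasticity | 10 | 30 | 1.50 | 78.5% |
| kPCr in two muscles + 4 fMRI | 6 | 18 | 0.90 | 60.3% |
| kPCr in one muscle + 4 fMRI | 5 | 15 | 0.75 | 53.7% |

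Counting elasticity as a single variable is an assumption. Multiple regressions could merge some of these tests or add others.

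**Step 2: allow for correlation.** Independence is not realistic: kPCr and Vmax, the two muscles, and the three walking tests are likely to move together. Data were simulated with no association between markers and outcomes, n = 30, an exchangeable correlation within each set, and 10,000 runs per setting. The chance of at least one two-sided p < 0.05 was:

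| Correlation, markers / outcomes (assumed) | m = 15 | m = 30 | m = 51 |
|---|---|---|---|
| 0.3 / 0.5 | 47% | 68% | 84% |
| 0.5 / 0.7 | 38% | 55% | 68% |
| 0.7 / 0.7 | 30% | 42% | 52% |
| 0.8 / 0.8 | 24% | 32% | 39% |
| 0.9 / 0.9 | 17% | 21% | 24% |

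Using 0.65 instead of 0.7 among outcomes in the second row changes the result by no more than about one or two percentage points.

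**Step 3: count only the hypothesised direction.** Assume one expected direction per marker, so each test has a 2.5% chance of a false link that way. Under independence this gives 1 − 0.975^51 = 72.5% and 1 − 0.975^18 = 36.6%. Simulated at 0.3/0.5, 0.5/0.65 and 0.7/0.8, the chance is 50%, 38% and 24% for 51 tests, and 28%, 22% and 15% for 18 tests. For 51 tests the share of the two-sided figure is 38/68 = 0.56 at 0.5/0.65 and 24/48 = 0.50 at 0.7/0.8, so about half.

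**Step 4: does the sample size matter?** With n = 15 and 51 tests, the five rows of Step 2 become 84%, 69%, 54%, 40% and 24%, almost unchanged. Sample size does not drive the false-positive rate. It does affect how a chance finding looks: at n = 30, p < 0.05 requires |r| of at least 0.36.

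**Step 5: would adjusting over everything work?** Bonferroni over 51 tests means p < 0.05/51 = 0.00098 and raises the critical |r| from 0.36 to 0.57. Error is controlled (simulated at 4.8% if independent, 3.4% at 0.5/0.7), but only very strong associations could be declared. Naming a few tests is the better route.

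**The case against.** The strongest reply is that this is a secondary objective in a small trial sized on pain free walking, and that the protocol already signals its lead marker. Section 3.6.3 treats the PCr resynthesis rate as the surrogate for mitochondrial function, and predicts that it will rise and go with better mobility. On that view the relevant family is 15 to 18 tests, the measures are correlated, and a link in the wrong direction would not be read as support. All of this has force, and it lowers the size of the problem. It does not remove it: section 3.6.3 states an expectation, not a test hierarchy, and section 9.1 applies the same threshold to everything.

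A reader might also go further than the documents allow, in three ways:

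- **That 51 regressions are planned, so a false link would appear in most repetitions of the trial.** Fifty-one is a count on the widest reading. It takes MRS in both muscles despite section 3.8, and it includes arterial elasticity, for which section 1.2 asks only about the drug effect. Even at 51, the chance falls below one half at high correlation, or at moderate correlation when only the hypothesised direction counts.
- **That the problem arises because there are only 30 patients.** Step 4 shows that it does not.
- **That all markers will enter one overfitted multiple regression.** Section 9.1 does not exclude this, but no section plans it.

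**Conclusion.** The concern holds in a limited form. Secondary objective 1 has no designated test, and the stated rule inflates the chance of a false mechanistic link on every reading examined. Over 15 to 51 pairings, the two-sided chance is about 54-93% under independence, about 38-68% at correlations of 0.5 among markers and 0.65 to 0.7 among outcomes, and about 17-24% at 0.9/0.9. The lowest of these is still more than three times the nominal 5% (17/5 = 3.4).

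These figures rest on three assumptions: the count of markers, exchangeable correlations that the documents do not give, and two-sided tests, since section 9.1 does not state sidedness. The point concerns a secondary objective and leaves the primary comparison untouched. It should be fixed, but it does not undermine the trial.

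**What to change.** Before unblinding, amend section 9.1 along these lines:

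- **Named tests.** Secondary objective 1 is tested with change in kPCr and one fMRI signal-change measure, each against change in pain free walking duration. kPCr follows section 3.6.3, and pain free walking is the construct used for sizing in section 9.2, there as a distance. The investigators choose the fMRI measure consistently with section 3.8.2, which links SE at 7T to small vessels and GRE to small and large vessels. The regression model and its covariates are stated.
- **Muscles.** Sections 3.6.1 and 3.8.2 want the two muscles examined separately. If that comparison is to be confirmatory, both muscles belong in the named set, giving 2 × 2 = 4 tests; with one muscle there are 2.
- **Adjustment.** Holm over the named tests: the smallest p value is compared with 0.05/2 = 0.025 for two tests, or 0.05/4 = 0.0125 for four.
- **Everything else.** All other pairings, including any other muscle or sequence and arterial elasticity against walking, are reported as exploratory estimates with 95% intervals and no claim of significance.
- **Reconcile** sections 3.6 and 3.6.1 with section 3.8 on whether MRS covers one muscle or two.

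The cost is a few lines of analysis plan, with no change to visits, measurements or sample size. The downside is that the remaining pairings, possibly including the muscle-specific comparison, become exploratory.

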9.2 Power analysis

Sample size for a double blind randomized clinical trial was determined using SAS version 9.3 (SAS Institute Inc., Cary, NC, USA). Sample size is based on the mean (SD) values obtain in a clinical trial that measured the effects of carperitide on pain free walking distance in patients with PAD 5. The mean (SD) pre post change in pain free walking distance was of 278 (240) m. [We have estimated that for a power 0.85 we will need 15 subjects per group to reject the null hypothesis with Type I error probability of 0.05] (Figure 6).

10 Clinical Management

[name] Assistant Professor in the Department of Medicine Division of Kidney Diseases and Hypertension will be the study physician for clinical trial. This includes adjusting the dose of Entresto (based on information obtain from the Entresto information sheet, Novartis), development of safety procedures and treatment of medical complications. The main PI ([name] MD PhD) will be the person directly in charge of admittance of patients into the study, performing and supervising the diagnostic tests and the metabolic, physiological and clinical functional testing.

11 Risks/Benefits

11.1 Potential Risks

As part of the PARADIGM-HF clinical trial adverse reactions occurring at an incidence of $\geq 5\%$ in patients who were treated with ENTRESTO in the double-blind period are shown in Table 2.

Table 2. Adverse effects and percentage of cases in the PARADIGM-HF.

Adverse effects	Entresto	Placebo + Enalapril	Preventive or corrective action
Angioedema, %	0.5	0.2	Discontinue
Hypotension, %	18	12	Dose adjustment of blood pressure lowering medications
Serious hypotension, %	1.5	1.5	Dose adjustment of blood pressure lowering medications
Renal failure, %	5	5	Monitor creat and blood urea
Hyperkalemia	12	14	Monitor K+
Cough, %	9	13	Modify dose
Dizziness, %	6	9	Prevent hypotension
Falls, %	1.90	1.30	Prevent hypotension

11.2 Methods to Minimize Risks

Patients will return to the clinic on weeks 2, 4 and 6 of the treatment period to assess for known adverse events and dosage adjustment if necessary. In addition, the clinical coordinator or the principal investigator will contact the subject by phone every other week to assess presence of adverse events and determine if an additional visit to the clinic is required. Patients will maintain a diary provided by the principal investigator to record blood pressure values and the date and time of the occurrence of known or unexpected adverse reactions. Subjects will be verbally warned and given a handout with a list of medications which are contraindicated or potentially cause an adverse interaction with Entresto. The medications on the list are on the Novartis information sheet on Entresto. The study physician and the PI will highlight these medications and the potential adverse events that can occur.

11.3 Emergency Procedures

Patients will be given detailed instructions of how to recognize any of the known serious or non-serious adverse events that may occur while receiving Entresto and also to report on previously unreported adverse events. If a non-life-threatening serious adverse events occurs, patients are advised to contact their primary care physician and then to contact the principal investigator. If there is a life threatening situation, subjects are advised to call 911 and then to contact the principal investigator. Patients will be given an emergency identification card with the contact information of the principal investigator and the name of the drug, to help inform the health care provider that this patient is in a clinical trial and may have been randomized to either Entresto or a placebo. In case of a serious adverse event, Entresto will be discontinued or dosage may be adjusted depending on the judgement of the study physician. All adverse events will be reported to the DSMB and their recommendations will be followed.

11.4 Unblinding Procedures in Case of Emergency

The Investigational Drug Services (IDS) pharmacy will generate the randomization schedule and will keep the clinical trial code stored in a secure location. The inpatient IDS pharmacy will hold the code, which can be access 24 hours, 7 days a week if necessary. The study physician and the main PI can have access to the code in case of a clinical emergency. The code will be revealed on request by the data safety monitoring board (DSMB) and at the completion of the clinical trial.

12 Ethical Considerations

12.1 Good Clinical Practice

The study will be conducted in accordance with the appropriate regulatory requirement(s). Essential clinical documents will be maintained to demonstrate the validity of the study and the integrity of the data collected. Master files should be established at the beginning of the study, maintained for the duration of the study and retained according to the appropriate regulations.

12.2 Institutional Review Board (IRB) Review and Informed Consent

The study will be conducted in accordance with ethical principles founded in the Declaration of Helsinki. The IRB will review all appropriate study documentation in order to safeguard the rights, safety and well-being of the patients. The study will only be conducted once IRB approval has been obtained. The protocol, informed consent, written information given to the patients, safety updates, annual progress reports, and any revisions to these documents will be provided to the IRB by the investigator.

A signed consent form will be obtained from the subject. The consent form will describe the purpose of the study, the procedures to be followed, and the risks and benefits of participation. A copy of the consent form will be given to the subject, and this fact will be documented in the subject's record. Research staff will ensure that candidates understand all elements of the consent form by addressing questions posed during the consent procedure and by asking for verbal confirmation that the candidate has no additional questions and verbally understands the purpose of the study, study intervention, basic procedures, risks, and that participation is voluntary. Subjects will be given as much time as they need to read and understand the consent form.

12.3 Confidentiality

All biologic specimens and clinical data obtained from this study will be linked to a study specific code and not to personal identifying information (e.g., name, social security number, medical record number). A key which will link the four-digit study code to the personal information will be maintained in a secure pass-word protected file maintained by the site study investigators.

All sites are committed to ensuring that appropriate measures are taken to protect the privacy and confidentiality of all Protected Health Information (PHI) for which it is responsible. This includes compliance with all regulations set forth by the relevant jurisdictions. In the US, this includes the HIPAA Privacy Rule, as well as with existing US State and Federal laws pertaining to PHI. All study volunteers in US will be given a copy of the Notice of Privacy Practices. Good faith efforts will be made to obtain each individual's written acknowledgement of receipt of the Notice(s). The rights mandated by the HIPAA Privacy Rule concerning an individual's ability to access, amend, and disclose certain sections of his or her own PHI will be fully respected, and every effort will be made to assist patients who choose to exercise these rights.

12.4 Declaration of Interests

Novartis is not funding this study and will play no role in the collection, analysis and interpretation of the data or the conduct of the study. None of the researchers have a conflict of interest to disclose regarding Entresto.

Appendix A: Contraindications from the American College of Sports Medicine

As most potential participants in this study will be a high-risk population for cardiovascular events, every exercise test is monitored using continuous EKG, blood pressure monitoring at rest, at each stage and for 6 minutes following the exercise test. The School of Nursing Exercise Laboratory is equipped with an automated defibrillator and has a standard procedure in place to respond to adverse events that may occur during the performance of an exercise test. Staff and the main PI will rehearse the emergency procedures twice a year and will have up to date CPR certifications. The main PI will supervise all exercise tests and will be responsible for following the guidelines outlined below.

The following are absolute and relative contraindications to initiate an exercise test

Absolute

1. A recent significant change in the resting EKG suggesting significant ischemia, recent myocardial infarction (within two days), or other acute cardiac event.
2. Unstable angina.
3. Uncontrolled cardiac dysrhythmias causing symptoms or hemodynamic compromise.
4. Symptoms of severe aortic stenosis.
5. Uncontrolled symptomatic heart failure.
6. Acute pulmonary embolus or pericarditis.
7. Suspected or known dissecting aneurism.
8. Acute systemic infection, accompanied by fever, body aches, or swollen lymph nodes.

Relative

1. Left main coronary stenosis
2. Moderate stenotic valvular heart disease
3. Electrolyte abnormalities
4. Severe arterial hypertension (e.g., systolic blood pressure > 200 mmHg and/or diastolic blood pressure > 110 mmHg) at rest.
5. Tachydysrhythmia or bradydysrhythmia.
6. Hypertrophic cardiomyopathy or any other form of outflow tract obstruction.
7. Neuromuscular, musculoskeletal, or rheumatoid disorders that are exacerbated by exercise.
8. High degree atrioventricular block.
9. Ventricular aneurism.
10. Uncontrolled metabolic disorders.
11. Chronic infectious disease.
12. Mental or physical impairment leading to inability to exercise adequately.

The following are absolute and relative indications to terminate an exercise test
Absolute Indications

1. Suspicion of a myocardial infarction or acute myocardial infarction (heart attack)
2. Onset of moderate-to-severe angina (chest pain)
3. Drop in systolic blood pressure (SBP) below standing resting pressure or drop in SBP with increasing workload accompanied by signs or symptoms
4. Signs of poor perfusion (circulation or blood flow), including pallor (pale appearance to the skin), cyanosis (bluish discoloration), or cold and clammy skin
5. Severe or unusual shortness of breath
6. CNS (central nervous system) symptoms
 1. e.g., ataxia (failure of muscular coordination), vertigo (An illusion of dizzying movement), visual or gait (pattern of walking or running) problems, confusion
7. Serious arrhythmias (abnormal heart rhythms)
 1. e.g.: second / third degree AV block, atrial fibrillation with fast ventricular response, increasing premature ventricular contractions or sustained ventricular tachycardia
8. Technical inability to monitor the ECG
9. Patient's request (to stop)

Relative Indications

1. Any chest pain that is increasing
2. Physical or verbal manifestations of shortness of breath or severe fatigue
3. Wheezing
4. Leg cramps or intermittent claudication (grade 3 on a 4-point scale)
5. Hypertensive response (SBP >260 mm Hg; DBP >115 mm Hg)
6. Pronounced ECG changes from baseline
 1. >2 mm of horizontal or down sloping ST- segment depression, or >2 mm of ST-segment elevation (except in aVR)
7. Exercise-induced bundle branch block that cannot be distinguished from ventricular tachycardia
8. Less serious arrhythmias (abnormal heart rhythms) such as supraventricular tachycardia
